8.2. Prior and Concomitant Medications

During the Run-In and Self-Practice Periods, the subject will use prophylactic medications as prescribed and rescue medications as needed and will document their use in the Migraine Diary.

 Neurolief Brain Innovation	THE RIME STUDY: ABRIDGED CLINICAL INVESTIGATION PLAN	Doc No.: CL-CIP-001 Abridged Ref Rev: REV.2 / 11JUN2019 Pg. 28 of 41
--	---	---

During the Treatment Period, the subject will continue his/her prophylactic medications and rescue medications as needed. While using the Relivion™ the subject will be asked to refrain from taking rescue medications/cannabis in the 4 hours prior to and 2 hours following each treatment.

8.3. Subject Consent

Informed consent will be obtained before any study-specific procedures are initiated or data collected. Principal Investigator or his/her authorized designee will conduct the informed consent process.

8.4. Randomization, Treatment Assignment and Blinding

Subjects will be prospectively randomized into the clinical study. Randomization will occur only after the subject provides informed consent, completes the Run-in Period and all required screening and baseline procedures, and satisfies the study eligibility criteria. Eligible subjects will be randomly allocated (with a 1:1 ratio) to one of the following 2 treatment groups based on a randomization scheme using the permuted block method stratified by center:

- Group A - active stimulation.
- Group B - sham stimulation.

The randomization scheme will be prepared by the study statistician using the SAS (version 9.4.) random number procedure. The block size will be random, and all study personnel will therefore be blinded to the randomization block size. Only the unblinded statistician /sponsor unblinding party and designees will be privy to the masked randomization scheme.

The Relivion™ Active and Sham devices will look the same and will be provided in the same packaging bearing the same labeling. Hence, both subjects and study personnel will remain blinded to the assigned treatment group.

8.5. Medication Compliance

While using the Relivion™ the subject will be asked to refrain from taking rescue medications/cannabis in the 4 hours prior to and 2 hours following each treatment. Subject will ascertain he/she did not consume any rescue medications/cannabis in the 4 hours prior to study treatment initiation. During each study treatment and up to 24 hours afterwards subjects will document any rescue medication/cannabis intake. PRO data of subjects who consumed rescue medications/cannabis will not be considered for the analysis of the related treatment time point.

 Neurolief Brain Innovation	THE RIME STUDY: ABRIDGED CLINICAL INVESTIGATION PLAN	Doc No.: CL-CIP-001 Abridged Ref Rev: REV.2 / 11JUN2019 Pg. 29 of 41
--	---	---

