	
 7. Subject has >10 headache days per month 8. Implanted metal/shrapnel or electrical devices in the head (not including dental implants), a cardiac pacemaker or an implanted or wearable defibrillator. 9. Received parenteral infusions for migraine within the previous 2 weeks. 10. Subject has known uncontrolled epilepsy. 11. History of neurosurgical interventions 12. Subject with implanted neurostimulators, surgical clips (above the shoulder line) or any medical pumps. 13. Current drug abuse or alcoholism. 14. Subject is participating in any other clinical study. 15. Skin lesion or inflammation at the region of the stimulating electrodes. 16. Personality or somatoform disorder. 17. Pregnancy or Lactation. 18. Women with child bearing potential without medically acceptable method of contraception (NOTE: Females of child bearing potential must have a negative pregnancy test). 19. Documented history of cerebrovascular event. 20. Subject with recent brain or facial trauma (occurred less than 3 months prior to this study). 21. Subject participated in a previous study with the Relivion device. 22. The subject does not have the basic cognitive and motor skills needed to operate a smartphone. 23. Subject with head circumference smaller than 51 centimeters or head circumference larger than 60 centimeters 24. Subject with other significant pain problem that in the opinion of the investigator may confound the study assessments.
Primary Efficacy Endpoint	
Proportion of subjects reporting reduction of migraine headache pain 2 hours post treatment initiation from severe or moderate to mild or no pain, or from mild to no pain, in their first eligible (per section 9.1.6) treated migraine attack, when using active combined occipital and supraorbital transcutaneous nerve stimulation compared to sham stimulation, in subjects suffering from acute migraine headache. Use of rescue medication prior to 2 hours post treatment initiation will be considered a failure for this end-point (i.e. patient will be assigned the status of no reduction).

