4.2. Endpoints

4.2.1. Primary Efficacy Endpoint

Proportion of subjects reporting reduction of migraine headache pain 2 hours post treatment initiation from severe or moderate to mild or no pain, or from mild to no pain, in their first eligible treated migraine attack, when using active combined occipital and supraorbital transcutaneous nerve stimulation compared to sham stimulation, in subjects suffering from acute migraine headache.

Use of rescue medication will be considered a failure for this end-point (*i.e.* patient will be assigned the status of no reduction).

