4.2.2. Secondary Efficacy Endpoints

1. Proportion of subjects reporting improvement in their MBS other than a headache, 2 hours post-treatment initiation (if rescue therapy was not used), in their first eligible treated migraine attack. MBS may be nausea, photophobia, phonophobia as defined by each subject prior to beginning of the treatment.
2. Proportion of subjects reporting reduction of migraine headache pain 1-hour post treatment initiation (if rescue therapy was not used), from severe or moderate to mild or no pain, or from mild to no pain, in their first eligible treated migraine attack.
3. Proportion of subjects who are pain free at 2 hours post treatment initiation (if rescue therapy was not used), in their first eligible treated migraine attack.

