- Subjects will be asked to refrain from consuming rescue medication/cannabis for at least 2 hours post treatment initiation. Subjects using rescue medication/cannabis prior to 2 hours post treatment initiation will be considered as failure (will be assigned the value of 0=no headache pain reduction) in the primary analysis.
- Subjects will document on the Patient Reported Outcome diary:
 - Pain according to a 4 points scale (0=no pain, 1=Mild pain, 2=Moderate pain, 3=Severe pain) at 1 and 2 hours \pm 30 minutes and at 24 hours \pm 6 hours post initiation of treatment.
 - Most Bothersome migraine-associated Symptom (MBS) other than a headache (chosen at baseline) improvement (yes/no) at 1 and 2 hours \pm 30 minutes post-treatment initiation.
 - Rescue medication intake.

8.1.7. Visit 4 - Termination visit (following 5 treated Migraine episodes or day 70 \pm 10, whichever comes first)

Written below are the assessments to be completed at Visit 4:

- After up to 5 migraine episodes within up to day 70 \pm 10, whichever comes first, subject will report to the clinic and return the device, Smartphone and hard copy subject diary, if applicable.
- Change in prophylactic anti-migraine & rescue headache medication will be documented.
- Subjects device Global Impression of Effect will be documented.
- Adverse events will be documented.
- Device logs, for each Migraine treated episode, will be downloaded by the study team (from study cloud database or from the device) to ascertain eligible treatments. An eligible treatment is defined as:
 - treatment meeting the basic criteria (*i.e.*, no analgesics or other pain relief drugs or cannabis within 4 hours period before the treatment initiation; no more than 30 minutes passed from the start of the migraine episode; more than 48 pain free hours have passed since subject's previous Migraine episode; and subject did not wake up with a Migraine headache); and
 - with total stimulation time of at least 30 minutes of a "pass" session on the device log timeline, where pass is defined as a minimal stimulation of 2mA delivered).

The characteristics of each treatment will be indicated on the subject CRF.

At this point subject's participation in this study will be over. The subjects will continue receiving medical care as per local standard of care, but not within the clinical study. Adverse Events that are still ongoing will be followed per local standard of care, but not within the clinical study.

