11.1. Study Endpoint Variables

11.1.1. Primary endpoint variable

The primary endpoint, the proportion of subjects reporting reduction of migraine headache pain 2 hours post treatment initiation from severe or moderate to mild or no pain, or from mild to no pain, in their first treated migraine attack, when using active combined occipital and supraorbital transcutaneous nerve stimulation compared to sham stimulation, in subjects suffering from acute migraine headache, will be measured in the form of a binary variable which will be assigned the value of "1" if the subject reports such headache pain reduction without having used rescue medications, and "0" otherwise. Rescue medication use within the 2 hours post treatment initiation will result in the subject will be coded as "0" automatically.

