11.1.2. Secondary endpoint variables

The three secondary endpoints will also be represented in the form of binary variables which will be assigned the value of "1" if the subject is a "responder" to each specific secondary endpoint, and "0" otherwise.

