Secondary efficacy endpoints include:

1. Proportion of subjects reporting improvement in their most bothersome migraine-associated symptom (MBS) other than a headache, 2 hours post-treatment initiation (if rescue therapy was not used), in their first eligible

treated migraine attack. MBS may be nausea, photophobia, phonophobia as defined by each subject prior to beginning of the treatment.

2. Proportion of subjects reporting reduction of migraine headache pain 1-hour post treatment initiation (if rescue therapy was not used), from severe or moderate to mild or no pain, or from mild to no pain, in their first eligible treated migraine attack.
3. Proportion of subjects who are pain free at 2 hours post treatment initiation (if rescue therapy was not used), in their first eligible treated migraine attack.

2.3

Additional efficacy endpoints

1. Proportion of subjects reporting freedom from their MBS other than a headache, 2 hours post-treatment initiation (if rescue therapy was not used), in their first eligible treated migraine attack.
2. Proportion of subjects who are pain free at 1-hour post treatment initiation (if rescue therapy was not used), in their first eligible treated migraine attack.
3. Proportion of subjects rating the subjects positive (score of 4 or 5) Global Impression of Effect of study device at the end of the study, defined as satisfied or very satisfied using a simple Likert-type scale whereas 1 = Very dissatisfied, 2 = dissatisfied, 3 = unsure, 4 = satisfied, 5 = Very satisfied.
4. Proportion of subjects reporting 2-24h headache relief, defined as headache relief at 2 hours without rescue medications, then no moderate to severe headache in the next 22 hours, and no use of rescue medication or additional stimulation.

Additional efficacy analyses that will be performed

1. Proportion of subjects reporting improvement in their MBS other than a headache AND reduction in their pain level, 1 and 2 hours post-treatment initiation (if rescue therapy was not used), in their first eligible treated migraine attack.
2. Proportion of subjects reporting freedom from their MBS other than a headache AND pain free, 1 and 2 hours post-treatment initiation (if rescue therapy was not used), in their first eligible treated migraine attack.
3. Rescue medicine usage.
4. Proportion of subjects who had pain relief in at least 50% of their eligible treated attacks at each timepoint.

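### Protocol 8.5 sets aside rescue users' diary data, against the rescue-is-failure rule stated for the primary endpoint, and leaves the scoring of the secondary and first two exploratory endpoints open to exclusion or imputation

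*Protocol*

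**What the plan says.** Protocol 8.5 (Medication Compliance) states, without naming or exempting any endpoint, that "PRO data of subjects who consumed rescue medications/cannabis will not be considered for the analysis of the related treatment time point".

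For the primary endpoint the plan says something else:

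- Synopsis, Primary Efficacy Endpoint: "Use of rescue medication prior to 2 hours post treatment initiation will be considered a failure for this end-point".
- Protocol 8.1.6: "Subjects using rescue medication/cannabis prior to 2 hours post treatment initiation will be considered as failure". The sentence goes on to limit this to the primary analysis.
- Protocol 11.1.1: "Rescue medication use within the 2 hours post treatment initiation will result in the subject will be coded as" zero.

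For secondary endpoint 3, Protocol 4.2.2 has only "pain free at 2 hours post treatment initiation (if rescue therapy was not used), in their first eligible treated migraine attack". Secondary endpoints 1 and 2 and exploratory endpoints 1 and 2 carry the same parenthesis. SAP 2.2 repeats it: "Proportion of subjects who are pain free at 2 hours post treatment initiation (if rescue therapy was not used"). Protocol 11.1.2 adds: "The three secondary endpoints will also be represented in the form of binary variables which will be assigned the value of" 1 for a responder and 0 otherwise. Protocol 11.1.3 does the same for the exploratory endpoints. Neither section mentions rescue users.

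Protocol 11.7.2 tests the three secondary endpoints with a Benjamini–Hochberg adjustment once the primary has reached p < 0.05. Protocol 11.7.5 allows missing secondary and exploratory data to be imputed. The SAP introduction gives the SAP precedence over the protocol.

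**The concern.** Setting aside a subject's data and counting that subject as a failure lead to different denominators. The failure rule is written for the primary endpoint only. Section 8.5 is the only general statement on what happens to rescue users' data, and it points away from failure coding. The parenthesis in the other endpoints can limit the numerator (a responder must not have used rescue) or the denominator (only subjects without rescue count).

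That leaves three possible outcomes for the secondary endpoints and exploratory endpoints 1 and 2: rescue users score 0, they leave the analysis, or their scores become missing and may be imputed. Rescue use happens after randomization and may itself reflect how the treatment worked. The second and third outcomes therefore condition a randomized comparison on a consequence of treatment. The choice should not stay open until the data are unblinded.

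**Working it through.** **The plan's own figure.** The point disputes no figure. For 45% against 25%, two-sided 5%, 80% power (Protocol 11.3), the pooled chi-squared formula gives n per arm = [1.960·√(2·0.35·0.65) + 0.8416·√(0.45·0.55 + 0.25·0.75)]² / 0.20² = (1.322 + 0.555)² / 0.04 = 88.1, so 89 per arm or 178 in all. The stated 90 per arm gives 80.8% power, and 180/0.90 = 200. The plan's 180 and 200 reproduce, and they rest on the primary endpoint.

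**Inputs for the illustration.**

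- 109 subjects with primary endpoint data (SAP introduction). An equal split is assumed, giving 54.5 per arm.
- 45% and 25%, borrowed from the primary endpoint (Protocol 11.3). The documents give no secondary-endpoint rates.
- Rescue fractions r of 5%, 10% and 20%, all assumed. The documents give none.

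**Effect on the difference.** A rescue user scores 0 under failure coding, so removing rescue users turns a failure-coded rate p into p/(1 − r) in each arm.

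| Rescue active/sham | Active | Sham | Difference (points) |
|---|---|---|---|
| Failure coding, any rescue | 45.0% | 25.0% | 20.0 |
| Exclusion, 5%/5% | 0.45/0.95 = 47.4% | 0.25/0.95 = 26.3% | 21.1 |
| Exclusion, 10%/10% | 0.45/0.90 = 50.0% | 0.25/0.90 = 27.8% | 22.2 |
| Exclusion, 10%/20% | 0.45/0.90 = 50.0% | 0.25/0.80 = 31.3% | 18.8 |
| Exclusion, 20%/10% | 0.45/0.80 = 56.3% | 0.25/0.90 = 27.8% | 28.5 |

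At other assumed rates the pattern is the same. In the order 10%/10%, 10%/20%, 20%/10%: for 20% against 10%, 10.0 points becomes 11.1, 9.7 or 13.9; for 60% against 40%, 20.0 becomes 22.2, 16.7 or 30.6. Imputing at each arm's rate among subjects without rescue gives the same expected differences as exclusion.

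**Effect on the error rate.** Take equal failure-coded rates in both arms and a two-sided 5% test (normal approximation, pooled variance under the null), with 54.5·(1 − r) subjects per arm. At rescue 20%/10% that is 43.6 and 49.05.

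- 25% response: 31.25% − 27.78% = 3.47 points; null standard error 0.0948, actual 0.0950. Rejection favouring active: P(Z > (1.960·0.0948 − 0.0347)/0.0950) = P(Z > 1.59) = 5.6%. Favouring sham: 1.0%. Total 6.6%.
- 50% response: 62.50% − 55.56% = 6.94 points; standard errors 0.1024 and 0.1020. Favouring active: P(Z > 1.29) = 9.9%. Favouring sham: 0.4%. Total 10.3%.

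At 10%/20% the two directions swap: rejection favouring active falls to 1.0% or 0.4%, below the nominal 2.5%, and the excess favours sham. Equal rescue in both arms causes no inflation. All these rates are before the Benjamini–Hochberg step and ignore the primary-endpoint gate.

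**The case against.** The strongest reply is that the documents already point to failure coding. The secondary objectives (Protocol 4.1.2) are worded as outcomes without rescue medication. Protocol 11.1.2 and 11.1.3 code everyone who is not a responder as 0. SAP 2.3, additional analysis 8, joins the same parenthesis to a denominator of all eligible treated attacks. The principal efficacy set is mITT (Protocol 11.6, SAP 4.3), which takes every subject who treats at least one eligible attack. Eligibility (SAP 2.1) bars analgesics and cannabis before treatment, not rescue afterwards, so a rescue user belongs to that set. Section 8.5 speaks of data rather than subjects and could mean only that the diary score is ignored and 0 assigned.

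This stands as evidence for the intended rule, and it lowers the weight of the point. It does not remove it. No sentence expressly scores rescue users on the secondary endpoints or on exploratory endpoints 1 and 2, and 8.5 as written says something different.

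Three stronger readings are tempting and not supported:

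- That the primary endpoint is in doubt. It is not: 8.1.6 and 11.1.1 are specific to it, and 8.5 is the outlier.
- That the plan has decided to exclude rescue users, or that exclusion would flatter the device. The text leaves the choice open, and the direction depends on which arm uses more rescue.
- That the full SAP lacks a rule. The visible SAP is abridged; one can say only that this text does not settle it.

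**Conclusion.** The concern holds as a wording conflict that should be fixed. Section 8.5 contradicts the failure rule on its plain reading. Applied to the formally tested secondary endpoints, it would remove or impute subjects on a post-randomization outcome. The primary endpoint and the sample size are unaffected. Exploratory endpoint 4 already builds rescue use into its definition of response, and the global impression is not tied to a treatment time point.

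Under the assumed rescue rates, a 20.0-point difference at 45% against 25% moves to between 18.8 and 28.5 points. It moves by only about 1 point if rescue is 5% in both arms. False rejection favouring active exceeds 2.5% only when rescue use is higher in the active arm. The sizes rest on assumed rescue rates, borrowed response rates and an equal split of 109. For the MBS endpoints the number per arm would be smaller, because Protocol 8.1.6 lets subjects record no MBS. Confidence is medium, because much of the text already favours failure coding and the full SAP is not visible.

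**What to change.** Before data lock, delete or replace the 8.5 sentence and add to the SAP:

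*For each responder endpoint, a subject (or attack) with rescue medication or cannabis use before the time point assessed is scored 0 at that time point, stays in that endpoint's denominator, and is not treated as missing or imputed. For MBS endpoints the denominator is defined by having an MBS recorded at baseline, regardless of rescue use.*

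The second sentence is needed because some subjects may record no MBS. Keeping every rescue user in the MBS denominator would otherwise make that denominator depend on rescue use.

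Apply the rule to the primary, secondary, exploratory and SAP additional responder analyses at every time point they name. That includes the 24-hour analyses (SAP 2.3, additional analyses 10 and 11) and those at each time point (4 to 9). Leave the 2–24h endpoint definition and the global impression unchanged. Name cannabis consistently in the scoring text.

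Separately, Protocol 8.1.6 counts the 2-hour abstention from treatment initiation, while 8.2 and 8.5 word it as following each treatment. The sponsor must reconcile these passages; no clinical rule is proposed here.

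The cost is a short SAP addition and one protocol deletion or replacement. The SAP prevails, so its text matters most. Rescue and cannabis use are already documented at 1, 2 and 24 hours (Protocol 8.6), so no new data are needed. The downside is lower responder rates than under exclusion, for example 45% instead of 50% at 10% rescue.

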8.6. Assessment of Efficacy

Efficacy parameters including Pain level, use of rescue medications/cannabis, presence and relief of most bothersome migraine-associated symptom other than headache will be documented during treatment at baseline, 1 hour, 2 hours and 24 hours.

These parameters will be documented by the subject using the diary (electronic or hard copy).

Treatment duration and intensity will be documented automatically in the device logs.

8.7. Assessment of Safety

Safety will be assessed by the collection of adverse events information from Enrollment (randomization) through study exit. Type, incidence, severity, duration, and procedure/device relationship of adverse events (AEs) will be collected throughout the study. Subjects with AEs at study exit will be followed for 14 days or until event resolves, whichever comes first. Adverse event data will be collected and reported on eCRFs.

9. Risks and Benefits

Risk management is performed as per ISO 14971, complete documentation is maintained on file (Neurolief document # QAD-022).

9.1. Risk Control and Mitigation

The following efforts will minimize risks to subjects in the study:

- Conduct of the study following successful completion of extensive bench performance testing and careful risk analysis.
- Selection of investigators who are experienced and skilled in management of patients with migraine.
- Establishment of a training program for study staff members (investigators and coordinator) and use of tools that will ensure proper training to the subjects for home use of the device.
- Clearly defining the inclusion and exclusion criteria such that only appropriate patients are enrolled in the study.

9.2. Risk-Benefit Rationale

Assessing the risks against the potential benefits of the use of the Relivion™ for alleviating migraine pain, Neurolief and the principal investigators have determined that there is a high likelihood that the expected benefit may outweigh the risk in patients fulfilling the study eligibility criteria.

10. Adverse Events and Device Deficiencies

Adverse event definitions used in this study are based on ISO 14155:2011 (Clinical Investigation of Medical Devices for Human Subjects -- Good Clinical Practice).

Adverse Events will be collected for all enrolled subjects with the point of enrolment (Visit #2) and end at the study termination visit (visit #4). Subjects with AEs at termination visit will be followed for 14 days or until event resolves, whichever comes first.

During the course of the study, all AEs will be collected and reported on the eCRF including:

- All AEs related to Relivion device and/or procedure
- All AEs not related to Relivion device and/or procedure
- All device deficiencies that may lead to a SAE
- All Deaths

